Any additional information relevant to the study should be included in the subject's source documents. In particular, any deviations from the study protocol or procedures should be recorded in the source documents.

For example, if study required procedures or visits are not completed or are completed outside the time frame specified in the protocol, the reasons for the departure should be explained in the source documents. The investigator must maintain all study documentation at least 2 years after the last approval of marketing application in and until there are no pending or contemplated marketing application or at least 2 years have elapsed since the formal discontinuation of clinical development of the investigational product. These documents should be retained for a longer period, however, if required by the applicable regulatory requirements (in Israel for 15 years) or by an agreement with the sponsor. The sponsor should inform the investigator in writing when the trial-related records are no longer needed.

Data Collection Method

Data from the subject's permanent medical records (see source documentation section) will be recorded on worksheets supplied by the investigator and approved by the sponsor. These worksheets (comprising the CRF's) will be used to transmit the information collected in the performance of this study to the clinical database either manually or by site data entry (a third party vendor may be used for this). CRF's should be filled no longer than 2 weeks after each visit. All worksheets must be typewritten or filled out in black ink, accurately and promptly following each examination or procedure. No questions will be left blank. Corrections will be made only by lining out (single line) incorrect data and writing in the revisions. All corrections must be initialed and dated by the individual performing/recording the correction. If the reason for the change is not obvious, an explanation for the change will be recorded. Blacking out or using correction fluid or an eraser will not be used to eliminate data. The investigator must review the worksheets for completeness and accuracy and must sign/date the forms where indicated. Signature stamps or substitutes are not acceptable. The investigator will retain originals of all source documents, subject consent forms, and study data as a permanent record. Each set of original worksheets should be reviewed for accuracy and completion (signatures, dates, adverse events, serious adverse events, protocol departures) and maintained in the investigator's study files.

16. QUALITY ASSURANCE AND QUALITY CONTROL

Monitors

Each study will be monitored by a representative of Venus Concept® at regular intervals throughout the course of the study according to a pre-defined monitoring plan. On site monitoring of the investigator's facilities aids in ensuring compliance with the protocol. Any deficiency noted during the monitoring visits will be discussed with the investigator and the corrective actions to be taken agreed upon. Should the sponsor determine, at any time during the study that the investigator is not in regulatory/protocol compliance, measures necessary to establish compliance will be implemented. If compliance cannot be maintained, the sponsor will suspend or terminate the study.

Device Use/Accountability

The evaluation site personnel will maintain records of the model and serial number of the devices (if appropriate) used for each treatment during the conduct of the study. If the clinic does not own the device to be used in this study, then it will be provided by Venus Concept for the duration of the study. The device and any additional equipment dedicated to the clinical study that was provided by the Sponsor will be returned to the Sponsor at the end of the study.

Training Requirements

Both the Investigator and the Sponsor, prior to any independent use of the device, will agree upon the Investigators' training requirements. Prior to the study, the Sponsor will ensure that each investigator has received in depth training on the use of the device.

17. ETHICAL AND REGULATORY CONSIDERATIONS

Ethical Conduct of the Study

The investigator is responsible for ensuring that this study is conducted according to the protocol, current International Conference on Harmonization (ICH) guidelines on good clinical practice (GCP), the latest revision of the 'Declaration of Helsinki', all applicable Federal and local government regulations.

An ethical committee will approve the clinical study protocol and related documents prior to site study initiation. Approval will be indicated in writing with reference to the final protocol number and date.

Details regarding the ethic committee constitution, including the names of its members, their qualification and what function they perform on the board, will be made available to enable Venus Concept® and the investigator to comply with internationally accepted guidelines governing good clinical research practices. A statement that the ethics committee is organized and operates according to GCP and the applicable laws and regulations must also be available.

This study will be conducted in compliance with the protocol after approved by Venus Concept® and site investigators. No deviation from the protocol will be implemented without the prior review and approval of Venus Concept® except where it may be necessary to eliminate an immediate hazard to a research subject. In such case, the deviation will be reported to Venus Concept® as soon as possible.

Sponsor's Obligations

A Sponsor must assume the following responsibilities and must keep the required records. The Sponsor must:

- Provide the Investigator with the necessary information - Protocol and Device User's Manual or Instructions for Use.
- Inform the Investigator of all new information that may affect his/her decision of whether to continue their participation in the study.
- Provide the supplies (Venus Viva™) for the investigation.
- Ensure the investigator is of good standing and knowledgeable in relevant areas of clinical research, including the protection of human subjects.
- Ensure that other site personnel have appropriate research experience and infrastructure to ensure adherence to the protocol and enrollment of sufficient evaluable subjects.
- Maintain the following records:
 1. A signed protocol and CRF
 2. All correspondence that relate to the clinical trial
 3. Signed Investigator Agreement
 4. Signed curriculum vitae (CV) and current medical license for all investigators and sub-investigators.
 5. Records of device shipment and disposal (shipping receipts, material destruction records, etc.)
 6. Other records as required by the Health Authority

Investigator's Obligations

Upon signing the protocol, the Investigator agrees to assume the following responsibilities;

- To keep the required records for a period of fifteen years following completion of the study
- To file the required reports in a timely manner:
- Conduct the Investigation in compliance with the protocol.
- Changes to the protocol may only be made after approval by the Sponsor, or when necessary to protect the safety, rights or welfare of a subject.
- Personally conduct or supervise the investigation.
- Read and understand the information in the Protocol and Investigator Brochure.
- Be aware of the potential risks and side effects of implanting the Venus Viva™ treatment.
- Ensure that all associates, colleagues and employees assisting in the conduct of the study are informed about their obligations.
- Inform all subjects that the device is being used for investigational purposes and ensure that the requirements related to obtaining the informed consent are met.
- Dispose of remaining supplies as directed by the Sponsor.
- Maintain the following records (for a period of 15 years following completion of the study):
 1. Signed copy of the protocol.
 2. Signed consent forms
 3. All correspondence as relates to the clinical trial
 4. Case Report Forms
- File the following reports:
 1. Severe adverse device related effects must be reported to the sponsor by phone within 24 hours. A written report must follow within five working days.

2. Unanticipated adverse device related effects must be reported to the sponsor as soon as possible, within 10 working days.
3. Deviations, which were made from the protocol for emergency use, must be reported to the sponsor as soon as possible, but no later than five working days after its occurrence.

Informed Consent Procedure

- In obtaining and documenting informed consent, the investigator should comply with the applicable regulatory requirements, and should adhere to GCP and HIPAA.
- Prior to the beginning of the trial, the investigator should have the Ethics Committee written approval/favorable opinion of the written informed consent form and any other written information to be provided to subjects.
- The written informed consent form and any other written information to be provided to subjects should be revised whenever important new information becomes available that may be relevant to the subject's consent. Any revised written informed consent form, and written information should receive the Ethics Committee's approval/favorable opinion in advance of use. The subject or the subject's legally acceptable representative should be informed in a timely manner if new information becomes available that may be relevant to the subject's willingness to continue participation in the trial. The communication of this information should be documented.
- Neither the investigator, nor the trial staff, should coerce or unduly influence a subject to participate or to continue to participate in a trial.
- The investigator, or a person designated by the investigator, should fully inform the subject or, if the subject is unable to provide informed consent, the subject's legally acceptable representative, of all pertinent aspects of the trial including the written information given approval/favorable opinion by the Ethic Committee.
- Before informed consent may be obtained, the investigator, or a person designated by the investigator, should provide the subject or the subject's legally acceptable representative ample time and opportunity to inquire about details of the trial and to decide whether or not to participate in the trial. All questions about the trial should be answered to the satisfaction of the subject or the subject's legally acceptable representative.
- Prior to a subject's participation in the trial, the written Informed Consent Form should be signed and personally dated by the subject or by the subject's legally acceptable representative, and by the person who is authorized to conducted the informed consent discussion.
- Prior to participation in the trial, the subject or the subject's legally acceptable representative should receive a copy of the signed and dated written Informed Consent Form and any other written information provided to the subjects. During a subject's participation in the trial, the subject or the subject's legally acceptable representative should receive a copy of the signed and dated consent form updates and a copy of any amendments to the written information provided to subjects.
- Subject or the subject's legally acceptable representative must provide informed consent and sign and date with his hand writing an Informed Consent Form (ICF) prior to any study related procedures being performed. The person reviewing the ICF with the subject must also sign and date the ICF. Each of the signers must sign and date in the presence of the other signer. If subject or the subject's legally acceptable representative is unable to comprehend and sign the Consent Form, subject must not be enrolled in the study.

18. STUDY COMPLETION

The PI will complete and report the study in satisfactory compliance with the protocol. It is agreed that, for any reasonable cause, either the PI or the sponsor, Venus Concept®, may terminate this study, provided a written notice is submitted at a reasonable time in advance of intended termination. If the study is terminated for safety reasons, the investigator will be notified immediately by telephone, followed by written instructions for study termination notification.

APPENDIX A

SUBJECT HOME TOLERABILITY SCALE- PROTOCOL CS0116

RETURN COMPLETED FORM AT NEXT CLINIC VISIT

Please circle the Score that best describes your tolerability of the study procedure.

Date: _____

Subject Tolerability Scale – 24hrs after Treatment	
Score	
(4)	Very Tolerable
(3)	Tolerable
(2)	Having no opinion
(1)	Intolerable
(0)	Very Intolerable

Please circle the Score that best describes your tolerability of the study procedure.

Date: _____

Subject Tolerability Scale – 3 days after Treatment	
Score	
(4)	Very Tolerable
(3)	Tolerable
(2)	Having no opinion
(1)	Intolerable
(0)	Very Intolerable

Subject Initials

DD-MMM-YYYY

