- The immediate responses, indicative of the desired effect, are erythema and edema in the immediate area of the stamp and possibly also around it. The edema usually appears 1-2 minutes post-treatment and reaches its peak (of up to moderate edema) within 30 minutes. It should be noted that erythema is not easily noticeable, if at all, in darker skin types, so the edema will indicate a more significant effect in these subjects.
- Treatment consists of a single pass over the designated area.
- Unless otherwise instructed, the energy parameters can be modified between the treatment visits, as per the Investigator's discretion.
- It is recommended that throughout the study, that one staff member administer the treatments and another staff member perform the evaluations of the treatment area.

Post Fractional RF Treatment

- Subject Discomfort Assessment recorded on a 100mm visual analogue scale (VAS) immediately post treatment.
- Subject Tolerability Scale immediately post treatment.
- Subjects will receive either the adjuvant combination treatment (SCR Complex™ followed by Bio Cel™ occlusive gel applied to the treatment area) or SOC (no topical applications to treatment for 24 hours post fractional RF treatment).
- Subjects will be asked to complete the Subject Home Tolerability Scale at 24 hours and 72 hours post-treatment
- Subjects will be provided with the Subject Home Instruction Sheet (Appendix B).
- A follow-up telephone call will be made to the subject 24 and 72 hours after the first treatment and 24 hours after the second treatment. Study staff will ask the subject to report on the treatment using the Self-Report Adverse Event Questionnaire (Appendix C) and remind the subject to complete and return to the clinic with their completed Subject Home Tolerability Scale at each visit.

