11.3 Follow-up/Termination Visit

Subjects will be scheduled for a follow-up/termination visit 72 hours after the second treatment. The following procedures will be performed:

- The subject will be asked to report on the comfort(s)/discomfort(s) associated with the second treatment as per the Self-Report Adverse Event Questionnaire.
- Wrinkle evaluation (Fitzpatrick Wrinkle and Elastosis Scale)
- Global Aesthetic Improvement (GAI) Scale (Appendix D) as evaluated by the investigator.
- Subject Tolerability Scale 72 hours post second treatment
- Assessment of concomitant medications

The subject's participation in the study is now complete. In case of early termination, the date and reason for early termination will be recorded in the CRF. Subjects will also be asked to return to the clinic to complete follow-up/termination visit procedures.

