14. STATISTICAL CONSIDERATIONS

Statistical Design

This study is a randomized, open-label, multi-centre study.

Sample Size

Enrollment will continue until up to 100 evaluable subjects have been recruited to the study. Any subject removed from the study in accordance with the provisions of this protocol will be replaced by other subject.

Statistical Methods

All subjects who received any amount of treatment will be included in the report. The primary outcome measure is the subject's overall tolerability of the adjuvant combination treatment as compared to the standard of care post fractional RF treatment. The self-assessment will be based on a 5-point Likert scale - Subject Tolerability Scale (Appendix A). Summary statistics will be generated for subject tolerability immediately after treatment, 24 hours and 72 hours following

treatment as per the terms: Very tolerable, tolerable, having no opinion, intolerable and very intolerable.

The secondary outcomes measures are the subject's degree of discomfort and/or pain as measured by the visual analogue scale (VAS), the incidence of spontaneous adverse events (AEs) and the investigator's assessment of improvement using the Fitzpatrick Wrinkle and Elastosis Scale scores before and after treatment as well as Global Aesthetic Improvement Scale (GAIS) for each subject. VAS scores from the treated group will be compared with the VAS scores of the standard of care group. The investigator's assessment of improvement using the Fitzpatrick Wrinkle and Elastosis Scale from the treatment group will be compared with that of the standard of care group. The GAIS scores for both groups will also be compared.

Summary statistics will also be generated for all treatment emergent adverse events (TEAs). The following types will be reported:

- Overall TEAEs
- Severe TEAEs
- TEAEs related to treatment
- Serious Adverse Events (SAEs)
- SAEs related to treatment
- TEAEs leading to treatment discontinuation

15. DATA HANDLING and RECORD KEEPING

Confidentiality

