APPENDIX C

Self-Report Adverse Event Questionnaire

Date:	___ / ___ / _____ <small>DD MMM YYYY</small>	Patient Code:	___ / ___ / _____ <small>Site # Pt. Initials Pt. #</small>
Have there been any changes in your health since your last visit?			Yes / No
If Yes, please describe the event in detail:			
Have there been any changes in your treatment area since your last visit?			Yes / No
If Yes, please describe the event in detail:			
Have there been any changes in your medications?			Yes / No
If Yes, please specify:			
Remind subject to complete the Subject Home Tolerability Scale.			Yes / No

Evaluator Name / Signature

DD-MMM-YYYY

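### Three of the four 24 h and 72 h primary tolerability scores sit on a take-home sheet, while staff phone at those hours without recording the score

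*Combined protocol and SAP*

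**What the plan says.** All references are to the combined protocol and SAP.

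- **Outcome.** Section 14: "Summary statistics will be generated for subject tolerability immediately after treatment, 24 hours and 72 hours following" treatment, in five ordered categories. It gives no rule for late or missing forms, and removed subjects are replaced.
- **Capture.** Section 11.2: "Subjects will be asked to complete the Subject Home Tolerability Scale at 24 hours and 72 hours post-treatment". The sheet in Appendix A carries the instruction "RETURN COMPLETED FORM AT NEXT CLINIC VISIT". Its 24 h and 3-day blocks each have a Date line but no time.
- **Calls.** Section 11.2: "A follow-up telephone call will be made to the subject 24 and 72 hours after the first treatment and 24 hours after the second treatment". On the call, staff go through the adverse event questionnaire and "remind the subject to complete and return to the clinic with their completed Subject Home Tolerability Scale at each visit".
- **Call form.** Appendix C asks about changes in health, treatment area and medications. It ends with a Yes/No tick against "Remind subject to complete the Subject Home Tolerability Scale". There is no field for the 0 to 4 score.
- **72 h after Tx 2.** Section 11.3 lists "Subject Tolerability Scale 72 hours post second treatment" among the follow-up visit procedures. The Synopsis also places it at that visit, and the Schedule of Events marks the scale there. Footnote 3 of the Schedule limits the home scale after Tx 2 to 24 h.
- **Early stopping.** Section 11.3 asks subjects who stop early to return for the termination procedures. Section 9 seeks final visit observations on withdrawal.

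**The concern.** The site speaks to each subject at the three times when a home score is due and does not write the score down. This leaves two weaknesses.

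**Late completion.** A sheet filled in shortly before Tx 2 holds a recalled score. Appendix B says that scabs usually form within 24 to 72 hours and shed 1 to 2 days later. Such a score would therefore usually be given after the acute reaction had passed.

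**Loss.** A subject who declines Tx 2 and does not attend the termination visit keeps both Tx 1 scores. Poor tolerability is a plausible reason to stay away, so the loss may depend on the outcome.

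These readings carry most of the arm comparison. Section 11.2 lists the immediate score before the adjuvant is applied. If that order is followed, the immediate score cannot reflect the adjuvant of that session. Section 8 has all subjects resume skin care at 24 hours, so the arms differ by protocol mainly in the first day. The 24 h score is then probably the most informative reading, and after both treatments it exists only on the home sheet.

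**Working it through.** The plan gives no figure to reproduce: no expected tolerability rates, no dropout rate and no derivation of the sample size.

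**1. Where each 24 h and 72 h score is captured**

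| Score | Source | Staff contact at that time | Score recorded by staff? |
|---|---|---|---|
| 24 h after Tx 1 | home sheet | call | no |
| 72 h after Tx 1 | home sheet | call | no |
| 24 h after Tx 2 | home sheet | call | no |
| 72 h after Tx 2 | follow-up visit | visit | yes |

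Three of four are home-only.

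**2. Delay before the site holds the score** (interval to the next visit minus the time at which the score was due)

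- Schedule of Events, Day 7 to Day 21: 21 − 7 = 14 days. The 24 h score arrives 14 − 1 = 13 days after it was due, the 72 h score 14 − 3 = 11 days after.
- Synopsis and Sections 5 and 11.2, three weeks: 21 − 1 = 20 days and 21 − 3 = 18 days.
- After Tx 2, follow-up at 3 days: the 24 h score arrives 3 − 1 = 2 days after it was due; the 72 h score has no delay.

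The 14-day and three-week statements must be reconciled; the point holds under either.

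**3. What outcome-dependent loss could do (illustration; all rates assumed)**

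Let p be the true proportion rating treatment intolerable or worse, q the share of those subjects' forms that is lost, and 5% the share lost among the others.

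Observed rate = p(1 − q) / [p(1 − q) + (1 − p) × 0.95]

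Assume p = 5% with the adjuvant and 15% with standard of care, a true difference of 10 points.

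- q = 25% in both arms: 0.0375/0.9400 = 4.0% and 0.1125/0.9200 = 12.2%; difference 8.2 points.
- q = 50% in both arms: 0.0250/0.9275 = 2.7% and 0.0750/0.8825 = 8.5%; difference 5.8 points.

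With 10% v 20% instead, and q = 10%, 30% or 50% in both arms, the 10-point difference becomes 9.6, 8.0 or 6.1 points.

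Now let loss differ by arm, again with 5% v 15%:

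- q = 50% with the adjuvant, 5% with standard of care: 2.7% v 15.0%; the difference widens to 12.3 points.
- q = 5% with the adjuvant, 50% with standard of care: 5.0% v 8.5%; it shrinks to 3.5 points.

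**4. How many forms this means**

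With an assumed 50 per arm, 2.5 + 7.5 = 10 subjects would rate treatment intolerable. Losing 25% to 50% of their forms is 2.5 to 5 forms in the whole trial.

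**The case against.** The case for leaving the plan as it is has substance.

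- **The calls are themselves a safeguard.** A reminder at the hour the score is due prompts completion on time, and each block of the sheet is dated. A reader might infer that nothing at all shows when a score was circled. That goes too far: a date exists. What stands is that the subject enters it and nothing checks it.
- **The calls do more than remind.** Poor tolerance can surface in the adverse event answers. That stands, but those answers are not the primary score and cannot replace it.
- **Loss is mitigated.** Termination visits and final observations are sought. Subjects who react badly to the test spot do not proceed (Sections 9 and 11.2), so intolerant subjects may be few. This reduces the risk; it does not recover a sheet that never comes back.
- **The illustration is assumed.** The documents give no rate of late or lost forms, and the plan summarises five categories rather than an intolerable/other split. This stands.
- **A spoken score has its own bias.** The trial is open-label, and no provision is made for callers unaware of the allocation. A rating given to staff may be more favourable than one circled in private, perhaps differently by arm. This stands, and it is why the spoken score should not simply replace the paper one.

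**Conclusion.** The point holds for three of the four 24 h and 72 h scores per subject. They are held only by the subject until the next visit, the calls at those hours do not record them, and there is no rule for late or missing sheets. The change is cheap and worth making; the gap does not by itself invalidate the comparison.

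Three stronger readings are not supported:

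- **That every 24 h and 72 h score depends on the home sheet.** The 72 h score after Tx 2 is taken at the follow-up visit, where there is no call.
- **That the primary endpoint is biased towards tolerable and the difference is shrunk.** The documents give neither the amount of loss nor its pattern. Shrinkage from 10 to between 8.2 and 5.8 points follows only if the same share of intolerant subjects' forms is lost in both arms. With unequal loss the difference can move either way.
- **That the plan truly requires two scores at 72 h after Tx 2.** The general instruction in Section 11.2 is not limited to Tx 1, but footnote 3 of the Schedule and the Synopsis show the intent. This is a drafting slip to tidy.

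The weight given to the home scores assumes that the order of steps in Section 11.2 is followed.

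**What to change.** 1. **Appendix C.** Add a field for the score, date and time. On the existing calls (24 h and 72 h after Tx 1, 24 h after Tx 2), the subject circles the score on the sheet and then reads it out; staff record it from a fixed script.
2. **Source rule in Section 14.** Keep the paper score as the source when it was completed on time. Use the call score when the sheet is missing or dated late. State in advance what counts as on time, and report by arm how many scores came from each source and how many are missing.
3. **Section 11.2.** Limit the 72 h home score to Tx 1, in line with footnote 3 of the Schedule of Events, so that the follow-up visit is the single source for 72 h after Tx 2. The instruction should not be deleted outright, because it also provides for the 72 h home score after Tx 1.
4. **Interval.** Reconcile the Tx 1 to Tx 2 interval between the Schedule of Events and the text.

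The cost is one question on each of three calls already planned, at most 3 × 100 = 300 across 100 subjects, with no added contact. The remaining drawback is that a score spoken to unblinded staff may be slightly more favourable, possibly differently by arm. Keeping the timely paper score as the source limits this.

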6. PRIMARY ENDPOINT

The primary outcome measure will be the tolerability of the application of the stem cell recovery complex (SCR Complex™) and a botanical lipid based occlusive (Bio Cel™) as compared with standard of care following fractional RF treatments.

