8. RANDOMIZATION

Subjects will be randomized to receive either standard of care (SOC) treatment (no topical therapy for 24 hours post fractional RF treatment) or a topical adjuvant combination treatment utilizing SCR Complex™ and Bio Cel™. The order of treatment will be assigned to subjects through subject number. All subjects will resume skin care as per VenusSkin protocol 24 hours post fractional RF treatments.

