11 STUDY PROCEDURES

Section 1, Schedule of Events, summarizes the type and frequency of each study procedure to be performed in this study.

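### The primary tolerability form asks about the study procedure, not the randomised after-care, so similar ratings in the two arms could not be read clearly

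*Combined protocol and SAP*

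**What the plan says.** Section 6 sets the primary outcome as the "tolerability of the application of the stem cell recovery complex" and Bio Cel, compared with standard of care (SOC). Section 14 describes it as the subject's "overall tolerability of the adjuvant combination treatment as compared to the standard of care" after fractional RF, and names the 5-point Subject Tolerability Scale in Appendix A as the instrument. Ratings are to be summarised immediately after treatment, at 24 hours and at 72 hours.

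Appendix A contains two items, headed 24 hours and 3 days after treatment. Each carries the same instruction: "Please circle the Score that best describes your tolerability of the study procedure". The headings and date lines show when the rating is made. Neither item says what period the subject should think back over.

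Section 8 defines the randomised contrast: either the adjuvant combination, or no topical therapy for 24 hours after RF. From 24 hours on, all subjects resume the same skin care protocol. Section 5 states that the study is open-label.

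**The concern.** The endpoint concerns what happens to the skin after RF under two kinds of after-care. The question put to the subject concerns a procedure. If subjects take that to be the RF session, they are rating something that both arms received alike and that was over before the after-care could act.

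What is at stake is mainly the reading of a null result. If the two distributions of ratings look alike, the report would be expected to say that the adjuvant is tolerated as well as SOC. The same data would arise if subjects in both arms had rated the RF session. Nothing else on the form separates these explanations, and no analysis can do so once the forms are in.

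**Working it through.** No stated figure bears on this point, so the check is of wording, followed by a short argument about size.

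**1. How the documents use the word 'procedure'.**

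| Place | What 'procedure' refers to |
|---|---|
| Section 3, Bio Cel paragraph | Occlusives belong to care given after the procedure, so the topical is separate from it |
| Section 10.2 | Bio Cel works after ablative and semi-ablative procedures: again separate |
| Section 9, inclusion criterion 2 | Ablation and resurfacing with Venus Viva |
| Section 2, statistical methodology | Discomfort following the procedure; section 11.2 takes the VAS immediately after treatment |
| Section 12, relatedness | Activity that supports use of the device |
| Section 11, opening | The Schedule of Events "summarizes the type and frequency of each study procedure to be performed in this study", which covers every scheduled activity |

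Five of the six uses point to the RF or device session, or set the topical apart from it. The sixth is broader and would take in the test spot, the RF session and the after-care together. None means the after-care alone. The subject's form does not define the term.

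**2. What else the subject reads.** The title of the home instruction sheet (Appendix B) names the topical adjuvant, which points towards after-care. The instructions beneath it use 'treatment' for the RF session, for example when saying how long afterwards scabs form. The Appendix A headings also count time from treatment. The cues are mixed.

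**3. Whether an item naming the adjuvant was possible.** SOC subjects receive no topical for 24 hours, so an item about the products could not be answered in that arm. A common item is needed. The only question is what it should point to.

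**4. What the wording does to the arm difference.** Let δ be the true difference between arms in how tolerable the after-care period is. Suppose a share p of subjects rate only the RF session, with no difference between arms, and the rest give an overall rating that carries δ in full. Then

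expected observed difference = (1 − p) × δ.

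- p = 0 gives δ: no dilution.
- p = 1 gives 0: complete dilution.
- If instead every subject adds the RF experience to the after-care experience, the difference stays δ and only the spread increases.

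The documents give no p, no δ, no standard deviation and no reason to prefer one of these models. The size therefore lies anywhere from none to complete.

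**5. Why no power figure is given.** Section 14 plans summary statistics for the primary outcome. It states no test, significance level, power or effect size, and no allocation ratio appears. The 100 evaluable subjects are an upper limit without a derivation. Any power loss would rest on invented inputs throughout.

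**6. Which period a better item must cover.** By section 8 the arms differ in the first 24 hours. At 72 hours, a look-back over the last 48 hours would run from 72 − 48 = 24 hours to 72 hours and miss that period entirely. A look-back to the end of the RF visit would include it.

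**The case against.** A reader might infer that the form measures the RF session and that the arm difference is therefore diluted. The documents do not support that. The term is undefined for subjects, section 11 uses it for any study activity, and the home sheet's title tells subjects that the study concerns a topical adjuvant. There is no evidence of how subjects would read the item.

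A global item is also a defensible choice. Section 14 speaks of overall tolerability, SOC subjects have no product to rate, and a shared rating compared between randomised arms can pick up an effect of after-care at 24 and 72 hours. If the RF experience simply adds to both arms, the mean difference is untouched.

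Rewording can do harm of its own. In an open-label trial, an item that mentions the after-care received would remind subjects of their allocation and invite expectation effects.

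Most of this stands. It reduces the claim from a demonstrated dilution to a possible one, removes any figure for its size, and limits what the new wording may say. It does not remove the ambiguity. On either reading the item fails to direct the subject to the period in which the arms differ, and a null result stays hard to interpret.

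**Conclusion.** The mismatch between the primary endpoint and the wording of its only instrument is in the text. The consequence is a risk: the arm difference may be diluted, and similar ratings could not be read clearly as equal tolerability of the after-care. How large the effect is cannot be derived from the documents. The point assumes only that some subjects could reasonably take the procedure to be the RF session, which most of the protocol's own usage supports.

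A reader might go further and infer a loss of power for the primary comparison. No such loss can be stated, because no primary test or power is planned.

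This is a cheap improvement to a form and does not show that the design fails.

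**What to change.** Before the first subject enters, reword both home items neutrally and identically in both arms. They should address the period after the RF session, include the first 24 hours, and name neither the products nor the assigned after-care. One wording that would serve on both the 24-hour and the 3-day form: *Rate how tolerable the condition of your treated skin has been since you left the clinic after your treatment.* The same wording should be used for the 72-hour rating collected at the follow-up visit after the second treatment.

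The change affects one existing page and adds no visit, subject or question. There are two costs. The home items may no longer match the immediate post-treatment rating, whose wording Appendix A does not show, so a change from that rating to 24 hours should not be read as a change on one scale unless the wordings are checked. The 3-day item also becomes cumulative: its 72-hour window contains the 24 hours already rated, and the two summaries should be labelled accordingly. Neutral wording avoids an extra cue to allocation but does not remove the expectation effects of an open-label design.
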